### Sample size

Due to the lack of results from previous similar research, a double-criteria approach described in the paper of Neuenschwander *et al* was used to calculate the required sample size in order to identify non-inferiority of laparoscopic versus open gastrectomy in terms of RFS. The first criterion was that the HR estimate was smaller than a critical threshold of 1.12, which corresponded to a difference of 8% in the 3-year RFS between two arms. As suggested by the paper, this number was chosen on the basis of clinical considerations. The second criterion required that the upper estimated one-sided 95% confidence bound of the non-inferiority margin was smaller than 1.59, which was calculated based on prior clinical research on laparoscopic gastrectomy after neoadjuvant chemotherapy, as well as on open gastrectomy after neoadjuvant chemotherapy.

On the basis of this approach, a sample size of 80 (40 per arm) is planned, with a type I error of 0.05 (two-sided) and a statistical power of 80%. The total sample size is 96 (48 per arm) after taking account of a 20% dropout rate in each group. The planned recruitment period is 2 years and the follow-up duration is 3 years.

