Intention-to-treat and per-protocol approach will be used for efficacy analysis. As-treated analysis will be applied for safety analysis. For variables with a significant amount of missingness, multiple imputations will be conducted for the purpose of sensitivity analysis. In terms of descriptive analysis, categorical data will be presented as number and percentage. Continuous variable will be presented as mean and SD if normally distributed, or as median and range otherwise. The primary analysis in this study aims to compare the 3-year RFS rate between laparoscopic and open gastrectomy after neoadjuvant chemotherapy. The date of recurrence is defined as the date of all-cause death or when a clinician judges recurrence

considering all information including serum tumour and the results of imageological examination. The RFS curves will be constructed as time-to-event plots using the Kaplan-Meier method. Log-rank tests will be used to make a simple comparison of the survival curves. Cox proportional hazards model will be performed to compare RFS after taking into account potential confounders. The overall survival will also be analysed in the same manner. Subgroup analyses will be conducted by age group, tumour location, body mass index category and TNM stage. All statistical analyses will be conducted in standard statistical software with a significance level of 0.05.

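### The sample size section gives one non-inferiority rule two different type I error levels: a one-sided 95% bound and a two-sided 0.05

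*Protocol*

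**What the plan says.** The protocol's Sample size section sets a two-part rule on the HR for RFS. "The first criterion was that the HR estimate was smaller than a critical threshold of 1.12". The second part requires that "the upper estimated one-sided 95% confidence bound of the non-inferiority margin was smaller than 1.59".

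The next paragraph takes the sample size from that rule: "On the basis of this approach, a sample size of 80 (40 per arm) is planned". The error level and power attached to that number follow in the same sentence: "with a type I error of 0.05 (two-sided) and a statistical power of 80" per cent. The total becomes 96 after a 20% allowance for dropout.

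The section Data collection and analysis ends with a general statement: "All statistical analyses will be conducted in standard statistical software with a significance level of 0.05". It gives no sidedness.

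**The concern.** An upper one-sided 95% bound is the upper limit of a two-sided 90% interval. Requiring it to lie below 1.59 is a test at one-sided 0.05. A two-sided 0.05 corresponds to the upper limit of a two-sided 95% interval, which leaves 0.025 in the one direction that matters for non-inferiority. The opening words of the sample size sentence tie the two together, so they cannot be read as belonging to separate tests. The unsided 0.05 in Data collection and analysis does not settle which was meant.

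At stake is the meaning of the 80% power. Strengths and limitations of this study describes the trial as adequately powered for non-inferiority in 3-year RFS and makes a possible phase III trial follow from that result. A reader cannot tell at which level the power was calculated.

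**Working it through.** **Inputs from the protocol.** Thresholds 1.12 and 1.59, one-sided 95% bound, two-sided 0.05, 80% power, 80 patients rising to 96 (Sample size); 1:1 allocation (Randomisation and blinding).

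**Inputs not in the protocol.** The assumed true HR, the control RFS and the event count. A true HR of 1 and the event counts below are therefore assumptions.

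**The plan's own figure.** 80 × 1.20 = 96 reproduces the total. The 80 itself cannot be reproduced, because those three inputs are missing.

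**Step 1: the two levels.** One-sided 0.05 has z = 1.645. Two-sided 0.05 has z = 1.960.

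**Step 2: what the difference does to the bound criterion alone.** With d events and equal arms, SE(ln HR) = 2/√d. Power is Φ((ln 1.59 − ln HR)/SE − z). For 80% power the first term must equal z + 0.842. Changing z then gives, for any true HR, control RFS or event count:
- 80% at one-sided 0.05, read at two-sided 0.05: Φ(1.645 + 0.842 − 1.960) = Φ(0.527) = 0.70.
- 80% at two-sided 0.05, read at one-sided 0.05: Φ(1.960 + 0.842 − 1.645) = Φ(1.157) = 0.88.

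**Step 3: which criterion binds.** The two criteria coincide at d = 4 × (z / ln(1.59/1.12))². That is about 88 events at one-sided 0.05 and about 125 at one-sided 0.025. Below those counts the bound is the stricter criterion; above them the 1.12 threshold is.

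**Step 4: power of the full rule.** The trial passes if ln(HR estimate) < c, where c = min(ln 1.12, ln 1.59 − z·SE). At a true HR of 1, power = Φ(c/SE).

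For 80 events, SE = 2/√80 = 0.2236:
- One-sided 0.05: c = 0.4637 − 1.645 × 0.2236 = 0.096, power = Φ(0.429) = 66.6%.
- One-sided 0.025: c = 0.4637 − 1.960 × 0.2236 = 0.025, power = Φ(0.114) = 54.5%.

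| Events (assumed) | Power, one-sided 0.05 | Power, one-sided 0.025 |
|---|---|---|
| 24 | 30.5% | 20.5% |
| 40 | 42.9% | 31.1% |
| 80 | 66.6% | 54.5% |
| 96 | 71.1% | 62.2% |
| about 221 | 80% | 80% |

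The last row is 4 × (0.842/ln 1.12)² ≈ 221. It is the same for both levels because the 1.12 threshold binds there.

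**Step 5: the true HR that would give 80%.** HR = exp(c − 0.842·SE).
- 40 events (SE 0.3162): about 0.72 at one-sided 0.05, or 0.66 at one-sided 0.025.
- 80 events: about 0.91 or 0.85.

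The protocol states no such assumption.

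**The case against.** The strongest defence is that the rule names its own bound, so the verdict can be reached without the type I error sentence. That stands. The decision rule is usable as written, and the fault lies in the level and power quoted for it.

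A second defence is that the extra 1.12 criterion might bring the rule's overall error down to 0.025, so that both statements are true. At a true HR of 1.59 this does happen, but only at about 125 events. With at most 80 events the error of the rule is 0.05, and with 96 it is 0.043. A trial of 96 patients cannot reach 0.025 by this route.

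A third defence is that the level makes no difference to the full rule, since about 221 events are needed either way at a true HR of 1. That is correct at that event count and true HR. At the event counts this trial can reach, the bound is the stricter criterion or nearly so, and the level does move the power.

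A stronger reading is tempting. The primary analysis is described thus: "The primary analysis in this study aims to compare the 3-year RFS rate between laparoscopic and open gastrectomy after neoadjuvant chemotherapy". A reader might infer that non-inferiority would be claimed from a non-significant log-rank test. The protocol does not say so. It calls the log-rank "Log-rank tests will be used to make a simple comparison of the survival curves", it states the rule under Sample size, and it plans a Cox model that can supply the HR and bound: "Cox proportional hazards model will be performed to compare RFS after taking into account potential confounders". Which model and analysis set carry the rule is commonly left to a statistical analysis plan, and its absence here is not an error.

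**Conclusion.** The contradiction is real and sits inside one section: one-sided 0.05 in the rule, 0.025 in the same direction in the sample size statement. It is worth correcting because the power claim rests on it.

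Its size depends on what is asked. For the bound criterion alone, 80% shifts to about 70% or 88%, with no further assumption. For both criteria at an assumed true HR of 1, neither level supports 80% with 80 patients, since events cannot exceed patients: at most 66.6% or 54.5%.

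Two inferences go too far. First, a reader might take the bound-only event counts at a true HR of 1, 4 × (1.645 + 0.842)²/(ln 1.59)² ≈ 115 against 4 × (1.960 + 0.842)²/(ln 1.59)² ≈ 146, as the trial's requirement. They leave out the 1.12 criterion. Second, a reader might conclude that the sample size of 80 is wrong under any assumption. A true HR below 1 could give 80% power, and the protocol does not say what was assumed.

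**What to change.** In Sample size, restate the type I error as one-sided 0.05, to match the bound already in the rule. Recalculate and state the power of the two-criterion rule at that level, with the assumed true HR, the control 3-year RFS and the expected number of events. In Data collection and analysis, give the sidedness of the 0.05 for the non-inferiority comparison.

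This needs no new data and leaves the decision rule unchanged. The cost is that the restated power may be below 80%, and the document should say so if it is. If the sponsor prefers 0.025, the bound must become one-sided 97.5%. That changes the decision rule and needs a dated amendment before the primary analysis.

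A cross-reference from Data collection and analysis to the rule in Sample size would help but is optional. The choice of Cox model, analysis set and role of the log-rank test remains with the sponsor.

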## ABSTRACT

**Introduction** Current guidelines recommend open gastrectomy with D2 lymph node dissection and adjuvant chemotherapy as the standard treatment for advanced gastric cancer. However, the prognosis is not satisfactory. Perioperative chemotherapy has been proposed to improve survival. Although still in debate, the efficacy of laparoscopic distal gastrectomy (LDG) in patients with advanced gastric cancer has been demonstrated in a few trials. Therefore, LDG after neoadjuvant chemotherapy can be a candidate for future standard treatment on advanced distal gastric cancer. We propose a randomised phase II trial to compare LDG and open distal gastrectomy (ODG) after neoadjuvant chemotherapy for advanced gastric cancer.

**Methods and analysis** To test the efficacy and safety, a randomised, open-label, single-centre, phase II trial was designed to evaluate the non-inferiority of LDG compared with ODG after neoadjuvant chemotherapy, with 3-year recurrence-free survival as the primary endpoint. The chosen critical value of a non-inferiority margin was an increase of <8%. The study started in 2015 and enrolled 96 patients according to a prior sample size calculation. Intention-to-treat and per-protocol approach will be used for efficacy analysis, and as-treated analysis will be applied for safety analysis. The survival curves will be constructed as time-to-event plots using the Kaplan-Meier method and compared using log-rank tests and Cox proportional hazards model. All statistical analyses will be conducted in standard statistical software with a significance level of 0.05.

**Ethics and dissemination** This study was approved by the Peking University Cancer Hospital Ethics Committee. The results will be submitted for publication in peer-reviewed journals.

**Trial registration number** NCT02404753; Pre-results.

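### The allowance for 20% dropout was made by multiplying 80 by 1.2. 96 patients retain about 77, not 80, at that rate; the effect is small.

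*Protocol*

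**What the plan says.** The Sample size section first gives the number required by its two-criterion design: "a sample size of 80 (40 per arm) is planned". It attaches to that number a two-sided type I error of 0.05 and 80% power. It then inflates for losses: "The total sample size is 96 (48 per arm) after taking account of a 20% dropout rate in each group". The Abstract carries the inflated figure forward, reporting that the study "enrolled 96 patients according to a prior sample size calculation".

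The protocol gives no other definition of dropout and no other inflation rule. Under Randomisation and blinding, patients are randomised only after neoadjuvant chemotherapy and a check of resectability. Under Data collection and analysis, efficacy is analysed both by intention to treat and per protocol, with Kaplan-Meier curves, log-rank tests and a Cox model for recurrence-free survival (RFS).

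**The concern.** A dropout rate in a group is a share of the patients who entered that group. To have a given number left after losing a fraction d, one divides by 1 − d. The stated total fits multiplication by 1 + d instead, which always gives too few.

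The protocol ties its power statement to 80 patients, and its Strengths and limitations section relies on that power for the non-inferiority question. If the planned dropout occurs, 80 patients with complete follow-up will not be there. The section therefore contains three figures (80, 20% and 96) that cannot all hold together.

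**Working it through.** **Inputs, all from the Sample size section**
- Required before dropout: 80 in total, 40 per arm.
- Dropout: d = 0.20 in each group.
- Stated after dropout: 96 in total, 48 per arm. Because this number is split by arm, I take it as the number randomised.
- Upper bound for the hazard ratio (HR): 1.59, one-sided 95%.

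**Step 1: reproduce the stated figure.** n × (1 + d): 80 × 1.20 = 96 and 40 × 1.20 = 48. Both match exactly.

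**Step 2: the inflation that retains 80.** n / (1 − d): 80/0.80 = 100 and 40/0.80 = 50. The stated total is 4 too low, 2 per arm.

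**Step 3: what 96 delivers.** 96 × 0.80 = 76.8 and 48 × 0.80 = 38.4 per arm. The shortfall against 80 is 3.2 patients, or 3.2/80 = 4%.

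**Step 4: the dropout that 96 does cover.** 1 − 80/96 = 0.167, so 80 remain if dropout is at most 16.7%.

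**Step 5: cost in power if dropouts contribute nothing.** The protocol gives no control RFS rate or event number, so I assume a true HR of 1 and that a fraction e of retained patients has an event. I use only the 1.59 bound at one-sided 0.05. Power ≈ Φ(√(n·e/4) × ln 1.59 − 1.645).

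| e (assumed) | n = 80 | n = 76.8 | Loss, points |
|---|---|---|---|
| 0.3 | 30.5% | 29.7% | 0.8 |
| 0.4 | 36.9% | 36.0% | 0.9 |
| 0.5 | 42.9% | 41.8% | 1.1 |
| 0.6 | 48.5% | 47.2% | 1.3 |

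Only the differences matter here, and they are about 1 percentage point throughout. The levels depend on the assumed e and are not an attempt to rebuild the protocol's 80%.

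**Step 6: events when dropouts are censored and not deleted.** Assume exponential event times and loss spread evenly over 3 years. For 3-year RFS S, the chance that a dropout has an event before loss is 1 − (1 − S)/(−ln S). At S = 0.60 this is 1 − 0.40/0.511 = 0.217. The 19.2 dropouts (96 × 0.20) then give 4.2 events and the 76.8 completers give 76.8 × 0.40 = 30.7, so 34.9 in total. Eighty fully followed patients would give 80 × 0.40 = 32. The same comparison is 43.8 against 40 at S = 0.50, and 26.1 against 24 at S = 0.70.

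**Step 7: break-even at S = 0.60.** The 96 reach 32 events if the dropouts supply 32 − 30.72 = 1.28 events, a chance of 1.28/19.2 = 0.067 each. With a yearly hazard of −ln(0.60)/3 = 0.170, that takes about 0.4 years of follow-up per dropout.

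**The case against.** The best defence accepts the arithmetic and disputes that it matters. Three arguments carry weight.

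First, a reader might infer from the shortfall that the primary analysis will have too few events, for example 31 instead of 32 at an assumed 3-year RFS of 60%. The protocol does not support that. The count of 31 deletes every dropout, whereas the planned intention-to-treat time-to-event analysis keeps each one until censoring. Steps 6 and 7 show that the event count can exceed that of 80 fully followed patients unless loss comes very early. This argument stands. The shortfall is a headcount of complete patients, and it bites mainly where patients are excluded, as in the per-protocol analysis.

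Second, 20% is a planning guess, the 16.7% that is covered lies close to it, and the protocol describes retention measures (repeated contact attempts and payment of travel costs). This is fair, but it defends the number of patients and not the sentence, which claims to have allowed for 20%.

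Third, the power for about 77 patients cannot be recomputed from the protocol, because the inputs behind 80 are not given. This also stands, so the restatement has to come from the sponsor. For the same reason, the power levels in Step 5 should not be read as showing that the base of 80 is wrong. That is a separate question, and this point takes 80 as given.

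Two possible escapes fail. Reading 20% as a share of the completers does not fit a rate described as applying in each group. Losses during chemotherapy do not explain the figure either, because randomisation comes after them.

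**Conclusion.** The stated total is wrong for the dropout rate it claims to cover: 100 would be needed, and 96 leaves about 77 complete patients. This follows from three figures in one section and needs no outside assumption beyond the ordinary meaning of a dropout rate. The repetition of 96 in the Abstract is the same figure carried forward, not a second error.

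The consequence is modest. It is a 4% shortfall in complete patients, and about 1 percentage point of power on the pessimistic assumption that dropouts add no follow-up, with a true HR of 1 and the 1.59 bound. The point warrants a correction to the text. It does not show that the intention-to-treat analysis will lack events, and it gives no reason to change the margin, the endpoint or the analysis.

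**What to change.** Keep enrolment at 96 and restate the last step of the Sample size section, for example:

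> Randomising 96 patients (48 per arm) leaves about 77 with complete follow-up if 20% drop out, or 80 if dropout is at most 16.7%.

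Say in the same place that the 80% power refers to 80 complete patients. The sponsor should add the power for about 77, computed from its own design inputs (the control RFS rate or the number of events), which the protocol does not give.

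The cost is one sentence and one recalculation by the sponsor. No patients are added and no analysis changes. The stated power becomes slightly less favourable.

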## Data collection and analysis

Trained oncologists collect data via datasheets on paper daily until the patient's discharge. Initial staging and therapeutic efficiency assessment include endoscopy, endoscopic ultrasound, non-contrast-enhanced CT scan of the thorax, and contrast-enhanced CT scan of the abdomen and pelvis. MRI examination will be used as an alternative to CT scan if the patient is allergic to radiocontrast agent or has other contraindications on CT examination. Laparoscopy and peritoneal washings for malignant cells are conducted before and after neoadjuvant chemotherapy. Tumour response evaluation after neoadjuvant chemotherapy includes both imageological and pathological examinations. The former is conducted according to the Response Evaluation Criteria in Solid Tumours (V.1.1). The latter is performed in accordance with the Tumour Regression Grade Standards of the National Comprehensive Cancer Network clinical practice guidelines in oncology for gastric cancer (V.3.2015). Gastrectomy specimens are open along the greater curvature, and macroscopic examination is conducted before representative blocks are taken from the tumour and its surrounding areas, and paraffin-embedded. All removed lymph nodes are embedded separately. Microscopic features are reported according to the seventh edition of the International Union Against Cancer TNM classification.

Information on prognostic status is collected via follow-up up to 3 years after the last treatment. Follow-up is conducted on a 3-month basis in the first 2 years and every half year in the third year. To promote participant retention and complete follow-up, three attempts are made to contact and remind the participants to come to the hospital for follow-up, and their transportation fees are covered by the research project. Every follow-up, participants receive physical examinations (ie, height, weight, Karnofsky score and others), laboratory tests (including blood cell test, blood biochemical test and serum tumour marker test) and imageological examinations (including ultrasonography, enhanced CT/MRI, endoscopy and chest radiograph). Tumour assessment will be conducted if recurrence is suspected, and further treatments such as surgery or chemotherapy will be performed when needed and will be recorded on the CRF. Data entry in EpiData is completed by two independent staff, with a third staff monitoring the quality.

Intention-to-treat and per-protocol approach will be used for efficacy analysis. As-treated analysis will be applied for safety analysis. For variables with a significant amount of missingness, multiple imputations will be conducted for the purpose of sensitivity analysis. In terms of descriptive analysis, categorical data will be presented as number and percentage. Continuous variable will be presented as mean and SD if normally distributed, or as median and range otherwise. The primary analysis in this study aims to compare the 3-year RFS rate between laparoscopic and open gastrectomy after neoadjuvant chemotherapy. The date of recurrence is defined as the date of all-cause death or when a clinician judges recurrence

considering all information including serum tumour and the results of imageological examination. The RFS curves will be constructed as time-to-event plots using the Kaplan-Meier method. Log-rank tests will be used to make a simple comparison of the survival curves. Cox proportional hazards model will be performed to compare RFS after taking into account potential confounders. The overall survival will also be analysed in the same manner. Subgroup analyses will be conducted by age group, tumour location, body mass index category and TNM stage. All statistical analyses will be conducted in standard statistical software with a significance level of 0.05.

## Data monitoring, auditing and interim analysis

Data monitoring and auditing are conducted by the funding agency annually. An interim analysis will be performed by an independent statistician when half of the patients have been randomised. The trial will be stopped if one treatment is found to be statistically more beneficial or harmful than the other.

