Laparoscopic gastrectomy has been used as a superior alternative to open gastrectomy to treat early gastric cancer. Although still in debate, the application of laparoscopic surgery in advanced gastric cancer has drawn increasing attention over the years. The most recent meta-analysis published in 2016 concluded that laparoscopic gastrectomy for advanced gastric cancer appeared to be comparable with open gastrectomy in the number of lymph nodes achieved, overall survival and disease-free survival, but had advantages over open gastrectomy in terms of faster postoperative recovery. However, 25 out of the 26 studies included in this analysis are retrospective, and randomised trials on laparoscopic versus open gastrectomy for advanced gastric cancer are scarce. Thus, more research providing higher level of evidence is needed.

It is therefore worthwhile to compare the safety and efficacy of laparoscopic and open gastrectomy when combining with neoadjuvant chemotherapy. There have been a few randomised trials comparing laparoscopic with open gastrectomy, and multiple on comparing gastrectomy with gastrectomy+neoadjuvant chemotherapy for advanced gastric cancer, but very few on the comparison between laparoscopic gastrectomy+neoadjuvant chemotherapy and open gastrectomy+neoadjuvant chemotherapy. To our best knowledge, only one similar trial was proposed to be carried out from 2011 to 2014 in Japan, but results have yet to be published. A retrospective study recently conducted by our team suggested that laparoscopic gastrectomy after neoadjuvant chemotherapy had comparable safety and efficacy as open gastrectomy in perioperative period. In particular, laparoscopic distal gastrectomy after neoadjuvant chemotherapy did not increase operation time, blood loss, postoperative complications and length of stay in the hospital compared with open gastrectomy. Additionally, patients in laparoscopy group can benefit from the shortened length of incision and faster recovery of gastrointestinal functioning. However, no significant difference was found between the two groups in proximal and distal margin, and the number of resected lymph nodes.

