### Outcomes

The primary endpoint is 3-year recurrence-free survival (RFS) rate. Recurrence includes any recurrence (local or regional, or distant) and death due to any cause (both gastric cancer and non-gastric cancer causes of death). The secondary endpoints are overall survival, radicalness of surgery, 30-day postoperative surgical morbidity and mortality, 2-week postoperative recovery index, cycles of

postoperative chemotherapy, and up to 1-year postoperative quality of life. The radicalness of surgery includes assessments on the number of lymph nodes retrieved and the length of resection margin. Postoperative complications are defined as complications occurring within 30 days after surgery, and will be classified according to the Clavien-Dindo classification system. Hospital mortality is defined as death occurring within 30 days after initial surgery, regardless of the cause. Postoperative recovery index considers blood loss, first aerofluxus time, first defaecating time, first time on a liquid diet, time of pulling gastric tube and drainage, and length of hospital stay. Postoperative pain intensity is measured by using a Visual Analogue Scale up to 72 hours after surgery. The time of applying intravenous patient-controlled analgesia and rescue morphine consumption is recorded. One-year postoperative quality of life is assessed using the European Organisation for Research and Treatment of Cancer (EORTC) Quality of Life questionnaires (QLQ-C30 and EORTC-QLQ-STO22).

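### The interim rule forces a stop on any statistical difference at 48 of 96 randomised, with only the blanket 0.05 to govern it; if RFS is tested, the two-sided difference test rejects in about 6–9%, not 5%

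*Protocol*

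**What the plan says.** Under *Data monitoring, auditing and interim analysis*, the protocol states: "An interim analysis will be performed by an independent statistician when half of the patients have been randomised". The consequence follows: "The trial will be stopped if one treatment is found to be statistically more beneficial or harmful than the other". The stop is mandatory and works in both directions. The section gives no endpoint, boundary or level.

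Two other places give a level. *Data collection and analysis* closes with: "All statistical analyses will be conducted in standard statistical software with a significance level of 0.05". It makes no exception for the interim. *Sample size* sets the design rate, "with a type I error of 0.05 (two-sided) and a statistical power of 80" per cent, and mentions no interim look.

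On timing, *Sample size* says: "The planned recruitment period is 2 years and the follow-up duration is 3 years". On the endpoint, *Outcomes* says: "The primary endpoint is 3-year recurrence-free survival (RFS) rate". Among the secondary outcomes, "Postoperative recovery index considers blood loss, first aerofluxus time, first defaecating time, first time on a liquid diet", together with other early measures. Describing the team's own retrospective study, the introductory text reports that "patients in laparoscopy group can benefit from the shortened length of incision and faster recovery of gastrointestinal functioning".

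**The concern.** The protocol fixes the timing, the trigger and the consequence of the look, and its one general level reaches that look unmodified. Read as written, the same difference could be tested twice at 0.05, so the stated 5% would not hold for that test.

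Timing the look by patients randomised is also a poor match for a 3-year endpoint. When the 48th patient is randomised, most of the first half have been followed for only months, so a mandatory stop would rest on a handful of events.

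Because the endpoint is not named, an early recovery outcome could also serve as the trigger. A stop on that ground would end recruitment at half size and leave the 3-year RFS question thinly answered.

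**Working it through.** **Inputs from the protocol.** 96 patients, 1:1, so the look falls at 96/2 = 48. Recruitment 2 years, follow-up 3 years. Log-rank test for RFS. Level 0.05, two-sided as in *Sample size*. Non-inferiority criteria: HR estimate below 1.12 and one-sided 95% upper bound below 1.59.

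**Assumptions.** The protocol gives no baseline RFS, so 3-year RFS (S3) is varied from 40% to 80%. Accrual is uniform, so the 48th patient arrives at about 1 year and mean follow-up at the look is about 6 months. RFS times are exponential.

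**Expected events.** With yearly hazard L = −ln(S3)/3, the look has 48 × [1 − (1 − e^−L)/L] events. For S3 = 60%, L = 0.170 and the result is 48 × 0.0805 = 3.9. With 3 years of follow-up per patient, the end has 96 × (1 − S3) events; for 60% that is 38.4. The information fraction is 3.9/38.4, about 10%.

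**Two looks at |z| > 1.96, no true difference** (simulated log-rank, 15,000 trials per column; simulation error about 0.2 percentage points):

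| Assumed 3-year RFS | 40% | 50% | 60% | 70% | 80% |
|---|---|---|---|---|---|
| Events at the look | 6.6 | 5.1 | 3.9 | 2.7 | 1.7 |
| Events at the end | 57.6 | 48.0 | 38.4 | 28.8 | 19.2 |
| Look rejects (%) | 4.4 | 4.3 | 3.2 | 2.3 | 1.1 |
| Final test alone rejects (%) | 5.1 | 5.2 | 5.3 | 5.3 | 4.9 |
| Either rejects (%) | 8.9 | 9.0 | 8.1 | 7.3 | 5.8 |

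The final test alone reproduces the stated 5%; adding the look does not. A larger run (100,000 trials, look fixed at 1 year, 24 per arm) gave 9.4/9.0/8.2/7.1% for 40–70%. The normal approximation, with correlation √0.1 between looks, gives 9.5%; the ceiling for independent looks is 1 − 0.95² = 9.75%. The simulated figures fall below this because events are sparse. With equal risk sets and all d events in one arm, z is about (d/2)/√(d/4) = √d. Three events cannot reach 1.96 (√3 = 1.73), but four can (√4 = 2).

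**What the look can detect.** At a true HR of 1.59 it would stop against laparoscopy in only 9.1/7.7/6.1/4.1% of trials (S3 40–70%).

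**Effect on the non-inferiority claim.** At a true HR of 1.59 and S3 = 60%, both criteria are met in 5.1% of trials without the look. The figure is 5.4% with it, counting a stop in favour of laparoscopy as success. Such stops occur in about 0.5% of trials across S3 40–70%, so the rise cannot be much larger.

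**A stringent threshold.** With p<0.001 at the look and 0.05 at the end, the normal approximation gives 5.1% overall at 10% information, and simulation gives 4.5–5.4%. By the same √d rule, p<0.001 (|z| > 3.29) needs about 11 events, all in one arm.

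**A stop on a recovery outcome.** With 48 patients and full 3-year follow-up, events are 48 × (1 − S3), exactly half of 96 × (1 − S3): for 60%, 19.2 instead of 38.4.

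**The case against.** The strongest reply is that the 0.05 at the interim is inferred. The interim has its own section, which says only that the difference must be statistical. A general 0.05 is compatible with an overall level that a boundary divides, and endpoint, boundary and spending are commonly left to a statistical analysis plan, which is not shown here. This stands in part: the protocol does not expressly set 0.05 for the look, so the 6–9% is conditional. It does not dispose of the point. The protocol itself fixes a mandatory two-way stop and a level for all analyses without exception, so an analysis plan with a proper boundary would have to override that wording.

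The second reply is that the inflated error belongs to a secondary comparison. That is right. A reader might take 6–9% as the error rate of the non-inferiority claim, because *Sample size* states 0.05 for that purpose. The calculation does not support this: the claim rests on the two HR criteria, whose error moves only from about 5.1% to 5.4%.

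The third reply is that recovery outcomes are nowhere named as the trigger. Also right. A reader might infer that the expected recovery benefit would probably end the trial, or that the rule fails whatever is tested. Neither follows. The retrospective advantage is given without a size, so any stopping probability would rest on an invented effect, and a look confined to safety would need no RFS adjustment. What stands is only that the wording leaves recovery outcomes open as a trigger.

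**Conclusion.** The point holds in conditional form. The rule is badly fixed: the stop is mandatory and two-way, timed by patients randomised, with an unnamed endpoint and only an unadjusted 0.05 to govern it.

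If RFS is tested at that level, the two-sided difference test rejects in about 6% (3-year RFS 80%) to 9% (40–50%) with no true difference, on about 2–7 interim events. These figures rest on assumed baseline RFS, uniform accrual and exponential times. The practical harm is limited: with no true difference, the look itself stops about 1–5% of trials, and the non-inferiority conclusion is nearly untouched. If a recovery outcome triggered the stop, about half the planned RFS events would remain; the likelihood of that cannot be judged from the protocol. The rule should be fixed, but it does not undermine the primary analysis.

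**What to change.** The *Abstract* reports 96 patients enrolled, so the look may well have passed; the change depends on whether it has.

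**If the look is still to come.** In *Data collection and analysis*, exempt the interim from the blanket 0.05. In *Data monitoring, auditing and interim analysis*, name the endpoint and require a stringent threshold for any RFS comparison. Two-sided p<0.001 keeps the overall rate near 5% with the final test still at 0.05. The alternative is an O'Brien-Fleming-type spending function at a look triggered by events; at the present timing (9.5–11.5% information for 3-year RFS of 70–40%) it would spend less than 1e-8. State that short-term recovery outcomes do not trigger stopping.

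**If the look has taken place.** Disclose the endpoint, the level and the result. Only if RFS was tested at 0.05, run the final log-rank or Cox difference test at the level that holds 0.05 overall, computed from the actual interim events. Under the assumptions above, that is a nominal 0.003/0.007/0.016/0.028 for 3-year RFS of 40/50/60/70%. Leave the two non-inferiority criteria unchanged. If RFS was not tested, say so; no RFS adjustment is needed.

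**Cost.** One rewritten paragraph and one clause, or one disclosure. An early RFS stop becomes very unlikely, which gives up little because the look has few events. If RFS was already tested at 0.05, the secondary difference test loses some power.
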